10.3. Withdrawal From the Use of Samples In Future Research

The patient may withdraw consent for use of samples for research (refer to Section 16.2.5). In such a case, samples will be destroyed after they are no longer needed for the clinical study. Details of the sample retention for research are presented in the main ICF.

11. STATISTICAL METHODS

Statistical analysis will be done by the sponsor or under the authority of the sponsor. A general description of the statistical methods to be used to analyze the efficacy and safety data is outlined below. Specific details will be provided in the Statistical Analysis Plan (SAP).

11.1. Patient Information

The primary and secondary efficacy analysis will be performed based on the intent-to-treat population, which will include all randomized patients.

Safety will be evaluated for the safety population, which includes all treated patients who receive at least 1 dose of randomized therapy. Subgroup analyses will be performed as appropriate, and details will be specified in the SAP.

Continuous variables will be summarized using descriptive statistics such as mean, standard deviation, and range. Categorical variables will be summarized using frequency tables. For time-to-event variables, the Kaplan-Meier method will be used for descriptive summaries.

The primary analysis will be conducted at 2-sided alpha level of 0.05.

11.2. Sample Size Determination

Based on previous reports of MRD negativity rate in lenalidomide-treated myeloma patients, as discussed in Section 3.2.1, the anticipated MRD (at 10^{-5}) negativity conversion rate is estimated to be 20% for patients treated by lenalidomide alone following post ASCT. Assuming a 20% absolute increase in MRD negativity rate (40% daratumumab plus lenalidomide versus 20% lenalidomide alone) by the end of 12-month maintenance treatment, a sample size of 214 patients (ie, 107 patients per treatment group at a 1:1 randomization) will be needed to achieve at least 85% power to detect such a treatment difference at a 2-sided alpha of 0.05 using continuity corrected chi-squared test.

Disease assessments for each patient will continue until 36 months from the date of randomization of last patient. It is anticipated that this will yield 64 PFS events and provide approximately 79% power to detect a 50% reduction in the risk of progression or death (HR=0.50, translating to an improvement in median PFS from 60 months to 120 months) with a log-rank test at a 2-sided alpha of 0.05 with an accrual period of 1 year. One interim analysis using Obrien-Fleming alpha spending function is planned at the time of primary endpoint analysis when approximately 32 events are anticipated.

11.3. Efficacy Analyses

Response to study treatment and PD will be evaluated by a validated computer algorithm based on IMWG 2016 criteria. There is no imputation planned for missing efficacy endpoint values.

11.3.1. Primary Endpoint and Analysis

The primary endpoint is the MRD conversion rate from baseline to 12 months after maintenance treatment as determined by NGS, which is the proportion of patients who have achieved MRD negative status [at 10⁻⁵] by 12 months after maintenance treatment prior to progressive disease (PD) or subsequent anti-myeloma therapy. Patients who have achieved MRD negative status on or after PD or switch to subsequent anti-myeloma therapy before PD, will not be considered MRD negative in the primary endpoint analysis.

The MRD conversion rate will be compared between the 2 treatment groups based on the intentto-treat population using the stratified Cochran Mantel-Haenszel test with baseline cytogenetic risk (high versus standard/unknown) as stratification factor. A Mantel-Haenszel odds ratio along with its 2-sided 95% CIs will be calculated.

11.3.2. Secondary Endpoints and Analysis

11.3.2.1. Progression-free Survival, Overall Survival, and Minimal Residual Disease

Time-to-event secondary endpoints including PFS and OS will be analyzed through a stratified log-rank test for the comparison of the distribution between the 2 treatment groups. The Kaplan-Meier method will be used to estimate the distribution for each treatment. The treatment effect (HR) and its 2-sided 95% CIs are to be estimated using a stratified Cox regression model

with treatment as the sole explanatory variable stratified by baseline cytogenetic risk (high versus standard/unknown).

The overall MRD negativity rate at any time after randomization and MRD durability will be analyzed.

The binary secondary endpoints including rate of CR and sCR will be analyzed similarly to MRD negativity rate.

A descriptive summary for duration of response will be provided. No statistical comparison will be made.

11.3.2.2. Patient-reported Outcomes

The EORTC QLQ-C30 and EORTC QLQ-MY20 scale scores and EQ-5D-5L utility and visual analog scores will be descriptively summarized by treatment group at each time point. Withingroup and between-group treatment effects of the PRO endpoints will be assessed by change from baseline using mixed models for repeated measures. Full details on meaningful change thresholds and statistical analyses will be provided in the SAP.

11.4. Safety Analyses

Adverse Events

The verbatim terms used in the eCRF by investigators to identify AEs will be coded using the Medical Dictionary for Regulatory Activities (MedDRA). Treatment-emergent adverse events are AEs with onset during the Treatment Phase or that are a consequence of a pre-existing condition that has worsened since baseline. All reported AEs will be included in the analysis. For each AE, the percentage of patients who experience at least 1 occurrence of the given event will be summarized by treatment group.

Summaries, listings, datasets, or patient narratives may be provided, as appropriate, for those patients who die, who discontinue study drug due to an AE, or who experience a severe or a serious AE.

Clinical Laboratory Tests

Laboratory data will be summarized by type of laboratory test. Reference ranges and markedly abnormal results (specified in the SAP) will be used in the summary of laboratory data. Descriptive statistics will be calculated for each laboratory analyte at baseline and for observed values and changes from baseline at each scheduled time point. Changes from baseline results will be presented in pre- versus post-treatment cross-tabulations (with classes for below, within, and above normal ranges). A listing of patients with any laboratory results outside the reference ranges will be provided. A listing of patients with any markedly abnormal laboratory results will also be provided.

Vital Signs

Descriptive statistics of pulse, temperature, and blood pressure (systolic and diastolic) values and changes from baseline will be summarized at each scheduled time point. The percentage of patients with values beyond clinically important limits will be summarized.

11.5. Benefit-risk Analyses

For benefit risk analyses, between-treatment differences will be shown with absolute rate or other difference measures and corresponding 95% CIs. Both continuous and dichotomized versions of continuous endpoints will be shown. Results will be displayed in tabular and forest plot form. Additional details will be provided in the separate benefit-risk SAP.

11.6. Interim Analyses

No interim analysis is planned for the primary endpoint of the study. The primary analysis will be performed after all randomized patients have completed 12 months of maintenance treatment, have disease progression, died, or have been discontinued/withdrawn from study treatment by this time point. Afterwards, an annual analysis will be performed to update secondary endpoints and safety. A final analysis will occur at the end of study 36 months from the date of randomization of last patient.

An interim analysis, at the time of primary endpoint analysis, and a final analysis will be conducted for PFS. Obrien-Fleming alpha spending function will be used to control overall alpha at 0.05.

11.7. Independent Data Monitoring Committee

An Independent Data Monitoring Committee, consisting of at least 2 clinicians and 1 statistician, will be established to review safety data before the primary analysis of the MRD negativity rate, which will be conducted by the sponsor. The Independent Data Monitoring Committee will start their review after the first 100 patients have been treated for at least 4 cycles or discontinued and subsequently perform their review every 6 months. Details will be provided in a separate Independent Data Monitoring Committee charter. Emerging data from all ongoing SC daratumumab studies will be communicated to the Independent Data Monitoring Committee, where applicable.

12. ADVERSE EVENT REPORTING

Timely, accurate, and complete reporting and analysis of safety information from clinical studies are crucial for the protection of patients, investigators, and the sponsor and are mandated by regulatory agencies worldwide. The sponsor has established Standard Operating Procedures in conformity with regulatory requirements worldwide to ensure appropriate reporting of safety information; all clinical studies conducted by the sponsor or its affiliates will be conducted in accordance with those procedures.

Method of Detecting Adverse Events and Serious Adverse Events

Care will be taken not to introduce bias when detecting adverse events or serious adverse events. Open-ended and nonleading verbal questioning of the patient is the preferred method to inquire about adverse event occurrence.

Solicited Adverse Events

Solicited adverse events are predefined local and systemic events for which the patient is specifically questioned.

Unsolicited Adverse Events

Unsolicited adverse events are all adverse events for which the patient is specifically not questioned.

12.1. Definitions

12.1.1. Adverse Event Definitions and Classifications

12.1.1.1. Adverse Event

An adverse event is any untoward medical occurrence in a clinical study patient administered a medicinal (investigational or non-investigational) product. An adverse event does not necessarily have a causal relationship with the intervention. An adverse event can therefore be any unfavorable and unintended sign (including an abnormal finding), symptom, or disease temporally associated with the use of a medicinal (investigational or non-investigational) product, whether or not related to that medicinal (investigational or non-investigational) product. (Definition per International Conference on Harmonisation [ICH])

This includes any occurrence that is new in onset or aggravated in severity or frequency from the baseline condition, or abnormal results of diagnostic procedures, including laboratory test abnormalities.

Note: The sponsor collects adverse events starting with the signing of the ICF (refer to Section 12.3.1, All Adverse Events, for time of last adverse event recording).

12.1.1.2. Serious Adverse Event

A serious adverse event based on ICH and EU Guidelines on Pharmacovigilance for Medicinal Products for Human Use is any untoward medical occurrence that at any dose:

- Results in death
- Is life-threatening (the patient was at risk of death at the time of the event. It does not refer to an event that hypothetically might have caused death if it were more severe.)
- Requires inpatient hospitalization or prolongation of existing hospitalization
- Results in persistent or significant disability/incapacity
- Is a congenital anomaly/birth defect

- Is a suspected transmission of any infectious agent via a medicinal product
- Is medically important*

*Medical and scientific judgment should be exercised in deciding whether expedited reporting is also appropriate in other situations, such as important medical events that may not be immediately life-threatening or result in death or hospitalization but may jeopardize the patient or may require intervention to prevent one of the other outcomes listed in the definition above. These should usually be considered serious.

If a serious and unexpected adverse event occurs for which there is evidence suggesting a causal relationship between the study treatment(s) and the event (eg, death from anaphylaxis), the event must be reported as a serious and unexpected suspected adverse reaction even if it is a component of the study endpoint (eg, all-cause mortality).

12.1.1.3. Unlisted (Unexpected) Adverse Event/Reference Safety Information

An adverse event is considered unlisted if the nature or severity is not consistent with the applicable product reference safety information. For daratumumab, the expectedness of an adverse event will be determined by whether or not it is listed in the Investigator's Brochure or package insert.

12.1.1.4. Adverse Event Associated With the Use of the Intervention

An adverse event is considered associated with the use of the study treatment(s) if the attribution is possible, probable, or very likely by the definitions listed in Section 12.1.2, Attribution Definitions.

12.1.1.5. Adverse Event Associated With Progression of Disease

Expected progression of disease should not be considered an adverse event (or serious adverse event). However, if determined by the investigator to be more likely related to the study treatment than the underlying disease, the clinical signs or symptoms of progression and the possibility that the study treatment is enhancing disease progression should be reported per the usual reporting requirements.

12.1.2. Attribution Definitions

Each adverse event is to be assigned an attribution definition, as shown below.

Not Related

An adverse event that is not related to the use of the intervention.

Doubtful

An adverse event for which an alternative explanation is more likely, for example, concomitant drug(s) and concomitant disease(s), or the relationship in time, suggests that a causal relationship is unlikely.

Possible

An adverse event that might be due to the use of study treatment(s). An alternative explanation, eg, concomitant drug(s) and concomitant disease(s), is inconclusive. The relationship in time is reasonable; therefore, the causal relationship cannot be excluded.

Probable

An adverse event that might be due to the use of study treatment(s). The relationship in time is suggestive (eg, confirmed by dechallenge). An alternative explanation is less likely, eg, concomitant drug(s) and concomitant disease(s).

Very Likely

An adverse event that is listed as a possible adverse reaction and cannot be reasonably explained by an alternative explanation, eg, concomitant drug(s) and concomitant disease(s). The relationship in time is very suggestive (eg, it is confirmed by dechallenge and rechallenge).

12.1.3. Severity Criteria

The severity assessment for an adverse event or serious adverse event should be completed using NCI-CTCAE Version 5. Any adverse event or serious adverse event not listed in the NCI-CTCAE will be graded according to investigator clinical judgment by using general guideline in the introduction of CTCAE Version 5:

Grade 1 (Mild):	Asymptomatic or mild symptoms; clinical or diagnostic observations only; intervention not indicated.
Grade 2 (Moderate):	Moderate; minimal, local or noninvasive intervention indicated; limiting age appropriate instrumental ADL*.
Grade 3 (Severe):	Severe or medically significant but not immediately life-threatening; hospitalization or prolongation of hospitalization indicated; disabling; limiting self-care ADL**.
Grade 4:	Life-threatening consequences; urgent intervention indicated.
Grade 5:	Death related to AE.

- * Instrumental ADL refer to preparing meals, shopping for groceries or clothes, using the telephone, managing money, etc.
- ** Self-care ADL refer to bathing, dressing and undressing, feeding self, using the toilet, taking medications, and not bedridden

The investigator should use clinical judgment in assessing the severity of events not directly experienced by the patient (eg, laboratory abnormalities).

12.2. Special Reporting Situations

Safety events of interest on a sponsor study treatment that may require expedited reporting or safety evaluation include, but are not limited to, the following:

- Overdose of sponsor study treatment. No maximum tolerated dose has been reached for daratumumab. However, if the dose exceeds the maximum tested dose of 2000 mg, then it will be considered as an overdose in this study.
- Suspected abuse/misuse sponsor study treatment
- Accidental or occupational exposure to sponsor study treatment
- Any failure of expected pharmacologic action (ie, lack of effect) of sponsor study treatment
- Unexpected therapeutic or clinical benefit from use of a sponsor study treatment
- Medication error involving a sponsor product (with or without patient/patient exposure to the sponsor study intervention, eg, name confusion)
- Exposure to sponsor study treatment from breastfeeding
- Special reporting situations should be recorded in the eCRF. Any special reporting situation that meets the criteria of a serious adverse event should be recorded on the serious adverse event page of the eCRF.

12.3. Procedures

12.3.1. All Adverse Events

All adverse events and special reporting situations, whether serious or non-serious, will be reported from the time a signed and dated ICF is obtained until 30 days (\pm 7 days) after the last dose of study treatment(s). The only exceptions are as follows (whichever occurs first):

- Patients who have withdrawn informed consent for study participation
- Patients who have received additional treatment with therapeutic intent for multiple myeloma within 30 days (\pm 7 days) after the last dose study treatment(s). For these patients, only adverse events that are considered to be possibly, probably, or definitely related to the study drug must be reported (unless the patient has been withdrawn from the study).

Serious adverse events, including those spontaneously reported to the investigator within 30 days (\pm 7 days) after the last dose of study treatment(s), must be reported using the Serious Adverse Event Form. The sponsor will evaluate any safety information that is spontaneously reported by an investigator beyond the time frame specified in the protocol.

Death and PD should not be recorded as an adverse event or serious adverse event but as the outcome of an adverse event. The event that resulted in the death should be reported as a serious adverse event.

All events that meet the definition of a serious adverse event will be reported as serious adverse events, regardless of whether they are protocol-specific assessments. Anticipated events will be recorded and reported as described in Attachment 2.

All adverse events, regardless of seriousness, severity, or presumed relationship to study treatment(s), must be recorded using medical terminology in the source document and the eCRF. Whenever possible, diagnoses should be given when signs and symptoms are due to a common etiology (eg, cough, runny nose, sneezing, sore throat, and head congestion should be reported as "upper respiratory infection"). Investigators must record in the eCRF their opinion concerning the relationship of the adverse event to study therapy. All measures required for adverse event management must be recorded in the source document and reported according to sponsor instructions.

The sponsor assumes responsibility for appropriate reporting of adverse events to the regulatory authorities. The sponsor will also report to the investigator (and the head of the investigational institute where required) all suspected unexpected serious adverse reactions (SUSARs). For anticipated events reported as individual serious adverse events, the sponsor will make a determination of relatedness in addition to and independent of the investigator's assessment. The sponsor will periodically evaluate the accumulating data and, when there is sufficient evidence and the sponsor has determined that there is a reasonable possibility that the intervention caused a serious anticipated event, they will submit a safety report in narrative format to the investigators (and the head of the investigational institute where required). The sponsor assumes responsibility for appropriate reporting of anticipated events to the regulatory authorities. The investigator (or sponsor, where required) must report SUSARs to the appropriate Institutional Review Board (IRB) that approved the protocol unless otherwise required and documented by the IRB.

For all studies with an outpatient phase, including open-label studies, the patient must be provided with a "wallet (study) card" and instructed to carry this card with them for the duration of the study indicating the following:

- Study number
- Statement, in the local language(s), that the patient is participating in a clinical study
- Investigator's name and 24-hour contact telephone number
- Local sponsor's name and 24-hour contact telephone number (for medical staff only)
- Site number
- Patient number
- Any other information that is required to do an emergency breaking of the blind

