treatment-emergent adverse events (TEAEs) was similar in both treatment groups (62.9% in the DRd group and 62.7% in the Rd group). Of the most frequently reported (>10%) Grade 3 or 4 adverse events, higher rates of neutropenia (DRd: 50.0%; Rd: 35.3%), lymphopenia (DRd: 15.1%; Rd: 10.7%), leukopenia (DRd: 11.0%; Rd: 4.9%), and pneumonia (DRd: 13.7%; Rd: 7.9%) were observed in the DRd group, while Grade 3 or 4 anemia occurred more frequently in the Rd group (DRd: 11.8%; Rd: 19.7%). Although Grade 4 TEAEs were reported in a higher percentage of patients in the DRd group compared with the Rd group, fewer patients in the DRd group (7.1%) discontinued study treatment due to a TEAE compared with the Rd group (15.9%); however, the percentage of patients discontinuing lenalidomide was similar in both arms.

The current study is being conducted to evaluate the MRD negativity conversion rate following the addition of daratumumab (compound number JNJ-54767414) to lenalidomide, when administered as maintenance treatment to patients with newly diagnosed multiple myeloma who have received a minimum of 4 cycles of induction therapy, have undergone HDT and ASCT within 12 months of the start of induction, are MRD positive at the time of screening, and have never been treated with an anti-CD38 antibody (ie, are anti-CD38 naïve). Further details on the overall rationale for the study, study design, assessments chosen for evaluation, and the potential risks and benefits are described in Section 3.2.

Throughout the protocol, the term "study treatment" refers to the treatments being administered for multiple myeloma and the term "sponsor" refers to the entities listed in the Contact Information page(s), which will be provided as a separate document.

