9.5.1. Adverse Events

Adverse events (excluding progression of multiple myeloma) will be reported by the patient (or, when appropriate, by a caregiver, surrogate, or the patient's legally acceptable representative) from the time a signed and dated informed consent is obtained until 30 days (\pm 7 days) following the last dose of any component of study treatment(s). Adverse events will be followed by the investigator as specified in Section 11.1.

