6.1. Adverse Events

All adverse events whether serious or non-serious, will be reported from the time a signed and dated informed consent form (ICF) is obtained until 30 days after the last dose of study treatment, until the subject withdraws consent for study participation, or until the subject starts subsequent antimyeloma therapy, whichever occurs first. Adverse Events will be recorded in standard medical terminology and graded according to the National Cancer Institute Common Terminology Criteria for Adverse Events (NCI-CTCAE), Version 5.0. The verbatim terms used in the eCRF by investigators to identify AEs will be coded using the latest Medical Dictionary for Regulatory Activities (MedDRA) coding dictionary.

Unless otherwise specified, at each level (e.g., system organ class and/or preferred term) of subject summarization in reporting the incidence of the AE, a subject is counted once if one or more events were recorded.

All summaries of AEs will be based on treatment-emergent adverse events (TEAEs). TEAEs are defined as any AE that occurs after start of the first study treatment through 30 days after the last study treatment, or the day prior to start of subsequent antimyeloma therapy, whichever is earlier; or any AE that is considered drug-related (very likely, probably, or possibly related) regardless of the start date of the event; or any AE that is present at baseline but worsens in toxicity grade during the TEAE reporting period, or after the TEAE reporting but is considered drug-related by the investigator. If the event occurs on the day of the first study treatment and either event time or time of study drug are missing, then the event will be assumed to be treatment-emergent. If the event date is recorded as partial or completely missing, then the event will be considered as treatment-emergent unless it is known to be prior to the first study treatment based on partial onset date or resolution date.

The following AE summaries will be presented by treatment group.

- An overview of TEAEs, including the number and percentage of subjects with
 - TEAEs
 - treatment-emergent SAEs
 - TEAEs related to study treatment
 - TEAEs leading to discontinuation of study treatment which includes those subjects indicated as having discontinued treatment due to an AE on the End of Treatment Disposition CRF page
 - TEAEs leading to discontinuation of any study treatment with action taken of drug withdrawn on AE CRF page

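### Adverse events are summarised as crude percentages although observation time follows time on treatment, so equal event hazards can appear as a difference of up to a few points between arms

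*Protocol*

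**What the plan says.** **Collection window.** Protocol 12.3.1 opens with "All adverse events and special reporting situations, whether serious or non-serious, will be reported from the time a signed and dated ICF is obtained" and closes the period 30 days (±7) after the last dose. Protocol 9.5.1 makes clear that the last dose of any component counts, so stopping daratumumab while staying on lenalidomide does not close the window. SAP 6.1 runs "until 30 days after the last dose of study treatment, until the subject withdraws consent for study participation", or until subsequent antimyeloma therapy starts, whichever is first. One exception is that SAP 6.1 also treats as treatment-emergent "any AE that is considered drug-related (very likely, probably, or possibly related) regardless of the start date of the event". Other malignancy and survival are followed beyond the window (Time and Event Schedule, Part 1).

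**Treatment duration.** Treatment continues to confirmed progression, unacceptable toxicity, withdrawal or the end of maintenance, with a maximum of 36 cycles of 28 days in both arms (Protocol synopsis).

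**Summary measure.** Protocol 11.4: "the percentage of patients who experience at least 1 occurrence of the given event will be summarized by treatment group". SAP 6.1: "a subject is counted once if one or more events were recorded". SAP section 6 contains no exposure-adjusted rate and no time-to-first-event analysis of adverse events. SAP 4.3 reports treatment duration and the number treated in each cycle, but only as exposure tables.

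**Time-structured tables that do exist.** Grade 3/4 TEAEs and SAEs are shown by cycle of first onset (SAP 6.1; for SAEs the bands are cycles 1-2, 3-6 and 7+). Infections are shown by onset up to 6, 6 to 12 and beyond 12 months (SAP 6.3.2).

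**Expected efficacy.** Protocol 11.2 assumes a PFS hazard ratio of 0.50, "translating to an improvement in median PFS from 60 months to 120 months".

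**The concern.** Progression ends treatment, and the end of treatment ends adverse-event observation 30 days later. If DR delays progression as the plan assumes, DR patients are at risk of a recorded event for longer. A percentage with at least one event grows with observation time, so it mixes the event hazard with the length of exposure.

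At stake is how the safety tables are read. A few points of difference in SAEs, Grade 3/4 events or infections could be taken as toxicity when it reflects longer treatment. A real difference could equally be masked if the exposure imbalance runs the other way. Crude percentages alone cannot separate the two.

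**Working it through.** **1. Reproduce the planning figures that drive the exposure difference (Protocol 11.2).**
- Power with 64 events at hazard ratio 0.50: z = (√64/2)·ln 2 − 1.96 = 2.773 − 1.960 = 0.813, giving 79.2% (stated: about 79%).
- Events with 107 per arm, exponential PFS, 12 months' uniform accrual and 36 months after the last patient: 107·[1 − (e^(−36λ) − e^(−48λ))/(12λ)] = 41.1 (R) + 23.0 (DR) = 64.1 (stated: 64).

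The PFS assumptions are therefore internally consistent and can be used as inputs.

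**2. Time on treatment if progression or death is the only reason to stop.**
- Cap T = 36 × 28 = 1008 days = 33.1 months. The tail is d = 30 days = 0.99 months.
- Stopping hazards: λ_R = ln 2/60 = 0.01155 and λ_DR = ln 2/120 = 0.00578 per month.
- Mean time on treatment, (1 − e^(−λT))/λ: 27.5 (R) and 30.1 (DR) months.
- Mean window including the tail: 28.5 and 31.1 months, ratio 1.09.

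**3. Crude percentage with the same constant event hazard h in both arms.**

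Percentage = 1 − e^(−hd)·[λ/(λ+h)·(1 − e^(−(λ+h)T)) + e^(−(λ+h)T)]

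For h = 0.02 per month:
- R: 1 − 0.9805 × [0.3661 × 0.6483 + 0.3517] = 42.2%
- DR: 1 − 0.9805 × [0.2241 × 0.5741 + 0.4259] = 45.6%

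| Setting (h equal in both arms) | R | DR | Gap, points |
|---|---|---|---|
| 36 cycles, h = 0.003 | 8.2% | 8.9% | 0.7 |
| 36 cycles, h = 0.02 | 42.2% | 45.6% | 3.4 |
| 36 cycles, h set so R = 30% | 30% | 32.5% | 2.5 |
| Treatment time capped at 12 months, R = 30% | 30% | 30.9% | 0.9 |

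The 12-month row is a simplification. At the primary analysis, patients enrolled early will have more than 12 months of treatment.

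**4. Can the direction change?** Suppose, as an assumption, that 30% of DR and 7.1% of R patients stop all treatment over 33.1 months for reasons other than progression. The mean windows are then 26.5 (DR) and 27.6 (R) months, ratio 0.96, and 30% on R corresponds to 28.9% on DR. The sign reverses.

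**5. Does an exposure-adjusted rate solve it?** With h = 0.02 throughout, first events per patient-month to first event or end of window are 0.4224/21.12 = 0.0200 (R) and 0.4563/22.82 = 0.0200 (DR). The ratio is 1.00, as it should be.

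Now let events cluster early, with the same hazard in both arms: 0.06 per month for 6 months, then none. The crude percentages are nearly equal (29.6% R, 29.9% DR). The rates are 0.2957/20.73 = 0.01427 and 0.2990/22.56 = 0.01325, a ratio of 0.93 that falsely favours DR. With a late hazard of 0.005 per month the ratio is 0.95. The rate should therefore not stand alone.

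**The case against.** The case against has several parts.

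- **No stated exposure difference.** No document says that DR patients will stay on treatment longer. The hazard ratio of 0.50 is a power assumption for progression or death. A reader might infer that the tables will show a false excess against daratumumab. The documents do not support that, because direction depends on actual time on treatment and step 4 gives a reversal. This part stands.
- **Size.** A reader might add the TEAE discontinuation rates that the Introduction quotes from the MAIA study (7.1% with daratumumab, 15.9% without) and reach a gap of 4.8 points (39.5% against 44.3% at h = 0.02). The same sentence of the protocol says that lenalidomide discontinuation was similar in both arms. Since the window here closes only after the last dose of any component, those rates cannot simply be carried over, and that study is in another setting. Applying 15.9% to both arms instead gives 39.5% against 42.5%.
- **Precision.** With 107 per arm, the standard error of a difference between 42% and 46% is about 6.8 points, a 95% half-width of about 13. The artefact is about half a standard error. No inferential safety analysis is planned, and early events such as injection reactions are hardly affected. This stands, but a systematic shift is not excused by imprecision.
- **Existing tables.** Onset-time tables cover the same three categories, and SAP 4.3 counts patients treated per cycle. The mitigation is partial. No at-risk denominator is specified for the onset tables, and the last bands (cycles 7+ for SAEs, beyond 12 months for infections) are open-ended, where exposure diverges most.
- **Exceptions to the window.** Drug-related events count whatever their start date, but unrelated SAEs and infections remain tied to the window.
- **Benefit-risk.** A reader might infer that the benefit-risk comparison would charge daratumumab with harm that comes from its efficacy. Protocol 9.6 and 11.5 leave the method to a separate plan that is not among these documents, and 11.5 does not confine it to crude percentages. That inference is unsupported.

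**Conclusion.** The point holds as a gap in the safety summaries, not as an error in the collection rule. Observation time depends on treatment time, the planned measure ignores it, and the plan's own PFS assumption implies about 9% longer observation on DR. At identical hazards the resulting difference is about 0.7 points at 8% incidence and 3.4 points at 42% over 36 cycles. It is smaller at the 12-month analysis and is limited throughout by the common 36-cycle cap.

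These figures assume exponential PFS with medians of 60 and 120 months, stopping for progression or death only, and a constant event hazard common to both arms. The actual direction and size are unknown until time on treatment is observed. That uncertainty is itself a reason to specify a time-adjusted summary in advance. No efficacy result, sample size or alpha is affected. This is a cheap improvement and not a threat to the trial's conclusions.

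**What to change.** In SAP 6.1 and 6.3.2, for SAEs, Grade 3/4 TEAEs and infections, keep the crude percentages and add by arm:

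- **(a) Cumulative incidence of first event at fixed times**, such as 12 and 24 months and the end of the 36-cycle period, censored at the end of the TEAE window and with death as a competing event. Thirty-six cycles plus 30 days is about 34 months (33.1 + 1.0), so an estimate at 36 calendar months would have almost no one at risk unless cycles are delayed.
- **(b) Exposure-adjusted first-event rate per patient-year with a 95% CI**: patients with a first event in the window, divided by time to that event or to the end of the window (the earlier of last dose + 30 days and the day before subsequent therapy). State how drug-related events after the window are handled, so that numerator and denominator match.

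State that (b) is to be read with caution when events cluster early, and that it should not be the only measure carried into the benefit-risk comparison.

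The cost is a few extra tables from dates the SAP already needs. Measure (b) assumes a roughly constant hazard. The censoring in (a) may be informative, because patients leave observation after progression or toxicity.
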